10.6 APPENDIX 6: CONTRACEPTIVE GUIDANCE AND COLLECTION OF PREGNANCY INFORMATION

It is acknowledged that only men will be enrolled in this study. Although women will not be enrolled, participants in this study may have female partners of childbearing potential. Therefore, sections have been included in this appendix to provide information relevant to women of childbearing potential (WOCBP) who may be partners of study participants.

10.6.1 Definitions

10.6.1.1 Woman of Childbearing Potential

A woman is considered fertile following menarche and until becoming post-menopausal unless permanently sterile (see below).

Women in the following categories **are not considered WOCBP**

1. Premenarchal
2. Premenopausal female with 1 of the following:
 - Documented hysterectomy
 - Documented bilateral salpingectomy
 - Documented bilateral oophorectomy

Note: Documentation can come from the site personnel's: review of the participant's medical records, medical examination, or medical history interview.

3. Postmenopausal female
 - A postmenopausal state is defined as no menses for 12 months without an alternative medical cause. A high follicle stimulating hormone (FSH) level in the postmenopausal range may be used to confirm a postmenopausal state in women not using hormonal contraception or hormonal replacement therapy (HRT). However, in the absence of 12 months of amenorrhea, a single FSH measurement is insufficient.
 - Females on HRT and whose menopausal status is in doubt will be required to use one of the non-estrogen hormonal highly effective contraception methods if they wish to continue their HRT while their partner participates in the study.

10.6.2 Contraception Guidance

Male participants with female partners of childbearing potential are eligible to participate if they agree to ONE of the following (during the protocol-defined time frame in the cohort appendix for each respective combination):

- Are abstinent from penile-vaginal intercourse as their usual and preferred lifestyle (abstinent on a long term and persistent basis) and agree to remain abstinent
- Agree to use a male condom plus partner use of a contraceptive method with a failure rate of <1% per year as described in [Appendix Table 6](#) when having penile-vaginal intercourse with a WOCBP who is not currently pregnant. In addition, male participants must refrain from donating sperm for the duration of the study and for 5 half-lives after the last dose of study intervention.

Male participants with a pregnant or breastfeeding partner must agree to remain abstinent from penile vaginal intercourse or use a male condom during each episode of penile penetration during the protocol-defined time frame and for 5 half-lives after the last dose of study intervention.

Appendix Table 6: Highly Effective Contraceptive Methods for Partner Use

Highly Effective Contraceptive Methods That Are User Dependent^a
Failure rate of <1% per year when used consistently and correctly.
Combined (estrogen and progestogen containing) hormonal contraception associated with inhibition of ovulation ^b 
 • Oral • Intravaginal • Transdermal
Progestogen only hormonal contraception associated with inhibition of ovulation 
 • Oral • Injectable
Highly Effective Methods That Are User Independent^a
Implantable progestogen only hormonal contraception associated with inhibition of ovulation ^b 
 • Intrauterine device (IUD) • Intrauterine hormone-releasing system (IUS) • Bilateral tubal occlusion
Vasectomized partner
A vasectomized partner is a highly effective contraception method provided that the partner is the sole male sexual partner of the WOCBP and the absence of sperm has been confirmed. If not, an additional highly effective method of contraception should be used.

Sexual abstinence

Sexual abstinence is considered a highly effective method only if defined as refraining from heterosexual intercourse during the entire period of risk associated with the study intervention. The reliability of sexual abstinence needs to be evaluated in relation to the duration of the study and the preferred and usual lifestyle of the participant.

NOTES:

- a) Typical use failure rates may differ from those when used consistently and correctly. Use should be consistent with local regulations regarding the use of contraceptive methods for participants participating in clinical studies.
- b) Hormonal contraception may be susceptible to interaction with the study intervention, which may reduce the efficacy of the contraceptive method. In this case, two highly effective methods of contraception should be utilized during the treatment period and for at least 5 half-lives after the participant's last dose of study intervention

10.6.3 Collection of Pregnancy Information from Male Participants with Partners who Become Pregnant

- The Investigator will attempt to collect pregnancy information on any male participant's female partner who becomes pregnant while the male participant is in this study. This applies only to male participants who receive study intervention.
- After obtaining the necessary signed informed consent from the pregnant female partner directly, the Investigator will record pregnancy information on the appropriate form and submit it to the Sponsor within 24 hours of learning of the partner's pregnancy. The female partner will also be followed to determine the outcome of the pregnancy. Information on the status of the mother and child will be forwarded to the Sponsor. Generally, the follow-up will be no longer than 6 to 8 weeks following the estimated delivery date. Any termination of the pregnancy will be reported regardless of fetal status (presence or absence of anomalies) or indication for the procedure.

10.7 APPENDIX 7: GENETICS

Use/Analysis of DNA

- Genetic variation may impact a participant's response to study intervention, susceptibility to, and severity and progression of disease. Variable response to study intervention may be due to genetic determinants that impact immune response, drug absorption, distribution, metabolism, and excretion; mechanism of action of the drug; disease etiology; and/or molecular subtype of the disease being treated. Therefore, where local regulations and IRB/IEC allow, a blood and tumor sample will be collected for DNA analysis from consenting participants.
- DNA samples will be used for research related to study intervention and/or mCRPC and related diseases or evaluation of new assay technologies. They may also be used to develop tests/assays including diagnostic tests related to study intervention and/or therapies of this drug class and/or immuno-oncology therapies and mCRPC. Genetic research may consist of the analysis of one or more candidate genes or the analysis of genetic markers throughout the genome or analysis of the entire genome (as appropriate).
- Stool samples will be collected, and microbiome nucleic acid extracted and analyzed to evaluate a participant's response to study intervention, susceptibility to, and severity and progression of disease. Variable response to study intervention may be due to bacterial genetic determinants that impact immune response, drug absorption, distribution, metabolism, and excretion; or by the mechanism of action of the drug.
- DNA samples may be analyzed for whole genome sequencing and bacterial DNA may be analyzed by 16s and/or whole metagenomic sequencing and relationship to clinical outcomes in response to study intervention. Additional analyses may be conducted if it is hypothesized that this may help further understand the clinical data and/or treatment of mCRPC.
- The samples may be analyzed as part of a multi-study assessment of genetic factors involved in the response to study intervention or study interventions of this class to understand study disease or related conditions.
- The results of genetic analyses may be reported in the clinical study report (CSR) or in a separate study summary.
- The Sponsor will store the DNA samples in a secure storage space with adequate measures to protect confidentiality.
- The samples will be retained while research on study intervention or study interventions of this class or indication (eg, immunotherapy) continues in accordance with applicable law.

10.8 APPENDIX 8: LISTS OF TERMINOLOGY AND ABBREVIATIONS

10.8.1 List of Terminology

Terminology	Description
Cohort	A group of participants receiving the same immunotherapy combination.
Cohort appendix	A document that guides the treatment of participants in a given cohort. The cohort appendices are identified using a letter designation (eg, Appendix Cohort A, Appendix Cohort B, etc.).
Core protocol	The master document that provides the elements common across the study and among all cohorts, unless otherwise specified.
Immunotherapy combination	Two or more study interventions administered to a cohort of participants.

10.8.2 List of Abbreviations

Abbreviation	Definition
ADA	anti-drug antibody(ies)
ADT	androgen deprivation therapy
AE(s)	adverse event(s)
AESI(s)	AE(s) of special interest
ALT	alanine aminotransferase
AST	aspartate aminotransferase
BCG	bacille Calmette-Guerin
BUN	blood urea nitrogen
C	cycle
Cmax	maximum observed drug concentration
cfDNA	cell-free deoxyribonucleic acid
CI(s)	confidence interval(s)
CIOMS	Council for International Organizations of Medical Sciences
CNS	central nervous system
COA	clinical outcomes assessment
CONSORT	Consolidated Standards of Reporting Trials
CR	complete response
CSR	clinical study report
CT	computerized tomography
CTC	circulating tumor cells

Abbreviation	Definition
CTC0	a measure of zero CTC
CTCAE	Common Terminology Criteria for Adverse Events
CTLA-4	cytotoxic T-lymphocyte-associated protein 4
DCR	disease control rate
DNA	deoxyribonucleic acid
ECG	electrocardiogram
ECOG	Eastern Cooperative Oncology Group
eCRF	electronic case report form
EDC	electronic data collection
EOT	end of treatment
FDA	Food and Drug Administration
FDG-PET	fluorodeoxyglucose positron emission tomography
FSH	follicle stimulating hormone
GCP	Good Clinical Practice
GnRH	gonadotropin-releasing hormone
GU	genitourinary
HIPAA	Health Insurance Portability and Accountability Act
HRQoL	health-related quality of life
HRT	hormone (hormonal) replacement therapy
I/E	inclusion/exclusion
IB	Investigator's Brochure
ICF	informed consent form
ICH	International Council for Harmonisation
IND	Investigational New Drug
INR	international normalized ratio
IRB/IEC	Institutional Review Board/Independent Ethics Committee
IUD	intrauterine device
IUS	intrauterine hormone-releasing system
IV	intravenous(ly)
LDH	lactate dehydrogenase
mCRPC	metastatic castration-resistant prostate cancer
MDSC(s)	myeloid-derived suppressor cell(s)
MMR	mismatch repair
MRI	magnetic resonance imaging
MSI	microsatellite instability
NCI	National Cancer Institute
NK	natural killer
NLCB	no longer clinically benefiting

Abbreviation	Definition
NLR	neutrophil/lymphocyte ratio
nmCRPC	nonmetastatic castration-resistant prostate cancer
ORR	objective response rate
OS	overall survival
OTC	over-the-counter
PAP	prostatic acid phosphatase
PBMC(s)	peripheral blood mononuclear cell(s)
PCWG2	Prostate Cancer Clinical Trials Working Group 2
PCWG3	Prostate Cancer Clinical Trials Working Group 3
PD	progressive disease
PD-1	programmed cell death 1
PD-L1	programed cell death ligand 1
PET	positron emission tomography

2 INTRODUCTION

The purpose of this document is to provide details of the planned analyses for PICI0033. The analyses specified in this document supersede the high-level analysis plan described in the protocol and its appendices. Statistical analyses will be performed consistent with the principles of the ICH/FDA Guidance for Industry E9 Statistical Principles for Clinical Trials.

3 STUDY DESIGN

[figure not shown]
PICI0033 is an open-label, non-randomized, exploratory platform protocol designed to assess the safety and antitumor activity of multiple immunotherapy combinations in participants with metastatic castration-resistant prostate cancer (mCRPC) who have received prior therapy. Each cohort of the platform study will consist of up to 2 stages: Stage 1, an initial stage to evaluate safety, biomarkers, and clinical activity of a combination and Stage 2, an expanded cohort, when warranted, based on the safety, clinical activity, and/or biomarker results from Stage 1. The Sponsor intends to modify and/or add new combinations to the protocol as data emerge from this and other trials.

This is not a randomized study. Assignment to one of the immunotherapy combinations will be made by the Investigator using his/her best clinical discretion based on the participant's medical history and disease status and knowledge of the available immunotherapy combination cohorts open for enrollment. The dose and schedule selected will be described in the protocol cohort appendix for each respective combination (eg, Appendix Cohort A, Appendix Cohort B, etc.). The duration of immunotherapy combination study intervention will be dependent on the combination administered. Participants will be followed for up to 2.5 years from the time of the initiation of study intervention.

The study is not intended or powered for hypothesis testing or comparison between cohorts. The study is intended to provide preliminary estimates of adverse event (AE) rates, response rates, effect sizes, and confidence intervals (CIs) to aid the design of later studies. Approximately 15 participants, including a minimum of 7 with a non-bone metastatic lesion that can be biopsied, will be enrolled in each immunotherapy combination cohort in Stage 1. An additional approximately 15 participants, including a minimum of 7 with a non-bone metastatic lesion, will be enrolled in Stage 2 if the cohort is expanded.

The general study schema is depicted in Figure 1.

Figure 1: Study Schema

3.1 Protocol Synopsis

Due to the platform design of this trial, there are multiple protocol levels. The Core Protocol contains information on study conduct that is uniform across all cohorts. Each cohort has a unique protocol appendix that describes study conduct and procedures that are unique to that particular immunotherapy combination. The Core Protocol and cohort-specific appendix should be used in conjunction with each other.

The Core Protocol Synopsis is included in Section 8.1.

3.2 Study Objectives and Endpoints

The study objectives and endpoints for the Core Protocol are listed in Table 1. Any cohort-specific endpoints will be captured in an appendix to this SAP.

Table 1: Objectives and Corresponding Endpoints

Objectives	Endpoints
Primary	

 To determine the safety of each immunotherapy combination in participants with mCRPC. 	
 Incidence and severity of AEs.
Secondary	

 To determine the CRR of each immunotherapy combination in participants with measurable mCRPC. 	
 Composite Response Rate (CRR): A composite endpoint where response is defined as a participant meeting at least one of the following:


• To determine the DCR of each immunotherapy combination in participants with measurable mCRPC.• To evaluate the rPFS of each immunotherapy combination in participants with mCRPC.• To estimate the OS of each immunotherapy combination in participants with mCRPC.	
◦ CTC response: Change from unfavorable (≥ 5 cells/7.5 mL of blood) to favorable (≤ 4 cells/7.5 mL of blood). Participants with a baseline CTC value < 5 cells/7.5 mL of blood will not be evaluated for this criterion.◦ PSA response: Confirmed PSA response is defined as $\geq 50\%$ reduction in PSA from baseline, with a repeat assessment confirming the result at least 3 weeks later. Participants without a baseline PSA assessment will not be evaluated for this criterion.◦ Objective response rate (ORR): Confirmed response of CR or PR by objective radiographic disease assessment using PCWG3-modified RECIST version 1.1 (ie, CR or PR and no progression in bone per the PCWG3; Scher et al., 2016). Per RECIST, to be assigned a best overall response of CR or PR, changes in tumor measurements must be confirmed by repeat radiographic assessments that should be performed no less than 4 weeks after the criteria for response are first met. Participants with measurable disease at baseline who received at least 1 dose of any component of the combination study intervention but do not have radiographic disease assessments for any reason will be counted as not responding. Participants without measurable disease at baseline will not be evaluated for this criterion.• DCR: Defined as the proportion of participants with CR, PR, or SD for 6 months as best response by PCWG3-modified RECIST v1.1. Participants with measurable disease at baseline who received at least 1 dose of any component of the study intervention combination but do not have RECIST assessment for any reason will be counted as not responding. Participants without measurable disease at baseline will not be evaluated for this endpoint.• rPFS: Defined as the time from initiation of study intervention to the first objective evidence of radiographic progression per PCWG3-modified RECIST v1.1 or death due to any cause (whichever occurs first).• OS: Defined as the time from initiation of study invention until death due to any cause.• OS rate at 12 months.
---	---

Exploratory	

• To evaluate tumor and immune biomarkers and their association with treatment outcome (antitumor activity and/or safety).• To estimate the radiographic DOR of each immunotherapy combination in participants with mCRPC.• To evaluate the PK of the components of the immunotherapy combination.• To evaluate the immunogenicity of the components of the immunotherapy combination.	
• Association of tumor and immune biomarkers from tissue, blood, and/or stool with clinical outcomes, including ORR, DCR, rPFS, and tolerability. Biomarkers to be studied will be chosen based on the immunotherapy combination.• Molecular characterization of CTC and evaluation of percent change from baseline.• Enumeration of CTC ≥ 1 at baseline with conversion to CTC0 on treatment.• PSA:
◦ Percent change in PSA from baseline at 12 weeks.◦ Maximum change in PSA at any point after initiation of study intervention.◦ Time to PSA progression, defined as the time from study treatment initiation to the date that a $\geq 25\%$ increase and absolute increase of ≥ 2 ng/mL above the nadir (or baseline value for participants who did not have a decline in PSA) in PSA. The increase must be confirmed by a second consecutive assessment conducted at least 3 weeks later.• DOR: Defined as time from the first tumor assessment that documents radiographic response (CR or PR) to the first documentation of radiographic progression per PCWG3-modified RECIST v1.1 or death due to any cause (whichever occurs first).• Sparse PK analysis.• Presence of ADA against biologic components of each immunotherapy combination.

ADA = anti-drug antibodies; AE = adverse event(s); CR = complete response; CRR = composite response rate; CTC = circulating tumor cells; CTC0 = a measure of zero CTC; DCR = disease control rate; DOR = duration of response; mCRPC = metastatic castration-resistant prostate cancer; ORR = objective response rate; OS = overall survival; PCWG3 = Prostate Cancer Clinical Trials Working Group 3; PK = pharmacokinetics; PR = partial response; PSA = prostate-specific antigen; RECIST = Response Evaluation Criteria in Solid Tumors; rPFS = radiographic progression-free survival; SD = stable disease

3.3 Determination of Sample Size

The study is not intended or powered for hypothesis testing or comparison between cohorts. The study is intended to provide preliminary estimates of AE rates, response rates, effect sizes and CIs to aid the design of later studies. A sample size of approximately 15 participants per immunotherapy combination cohort will provide these preliminary estimates while limiting exposure.

Table 2 provides 95% exact confidence intervals for the proportion of participants experiencing a specific AE for sample sizes of 15 and 30 participants per cohort. These confidence intervals, along with the CRR (described below), provide information needed to assess the risk-benefit ratio of the immunotherapy combination for expanding the cohort to Stage 2 and for the design of further studies.

Table 2: Confidence Intervals for the True Proportion of Adverse Events

Observed AE rate	95% Confidence Interval (n = 15)	95% Confidence Interval (n = 30)
6.7% (1/15 or 2/30)	(0.2%, 31.9%)	(0.8%, 22.1%)
13.3% (2/15 or 4/30)	(1.7%, 40.5%)	(3.8%, 30.7%)
20.0% (3/15 or 6/30)	(4.3%, 48.1%)	(7.7%, 38.6%)
26.7% (4/15 or 8/30)	(7.8%, 55.1%)	(12.3%, 45.9%)
33.3% (5/15 or 10/30)	(11.8%, 61.6%)	(17.3%, 52.8%)
40.0% (6/15 or 12/30)	(16.3%, 67.7%)	(22.7%, 59.4%)

AE = adverse event

A Simon two-stage minimax design (Simon, 1989) will be implemented for each cohort. A CRR of at least 25% would provide sufficient evidence of clinical activity to warrant further investigation, while a CRR of 10% would not be of interest. In Stage 1, 15 participants will be enrolled. If the safety profile is acceptable and there are 2 or more responses in these 15 participants, 15 additional participants may be enrolled in Stage 2 for a total of 30 participants in the cohort. If there are 6 or more responses in these 30 participants, then the immunotherapy combination will be considered worthy of further investigation. This design yields a type I error rate of 0.07 and 77% power when the null hypothesis assumes the CRR is 10% and the alternative hypothesis assumes the CRR is 25%. Under the null hypothesis, the probability of terminating a cohort after Stage 1 is 55%.

3.4 Analysis Timing

The primary analyses described in the main body of this document will be performed for each immunotherapy combination cohort separately after all participants for a specific cohort have at least 6 months of follow-up from the date of first dose or have discontinued the study. Each cohort will be assessed independently of the other cohorts, and the data from each cohort will be analyzed separately. Study conduct of one or more cohorts may be ongoing at the time of final analysis for a given cohort.

Any cohort-specific modifications to the statistical methods, including any additional cohort-specific endpoints, will be captured as an appendix in this SAP.

Analysis of safety and efficacy endpoints will be performed prior to the time of primary analysis. These analyses will help inform adaptations of the trial, such as expanding, modifying, or terminating a cohort. More information about these interim analyses is presented in Section 5.7. These results may be presented and/or published prior to the primary analysis.

A cohort will formally end once all participants have been followed for survival status for a maximum of 2.5 years or until death, withdrawal of consent, or loss to follow-up. The Sponsor may choose to discontinue survival follow-up of a cohort at any time. A survival analysis of long-term follow-up may be performed after the primary analysis has been completed.

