1.3 SCHEDULE OF ACTIVITIES

The Schedule of Activities (SOA) shown in [Table 1](#) provides a general overview of the types and timing of the tests and procedures that will be performed in this study. The combination-specific tests and procedures, as well as the timing, will be described in the cohort appendix for each respective combination and will supersede the general overview provided here.

Table 1: Schedule of Activities

Tests & Procedures	Screening/ Enrollment ^a	On-Treatment: Immunotherapy Combination Treatment					End of Treatment ^b	Follow up	
		Cycle 1	Cycle 2	Cycle 3	Cycle 4	Cycle 5 Onward			
Day		To be determined based on immunotherapy combination Refer to the cohort appendix for each respective combination for details on combination-specific timing							14 - 28 days after last dose
Window (days)	-28		± 3	± 3	± 3	± 3	± 7	± 10	± 14
Informed consent ^d	X								
Review of I/E criteria	X								
Medical and cancer history	X								
Physical examination	X	X	X	X	X	X	X		
ECOG performance status	X	X	X	X	X	X	X	X	
Vital signs (see Section 8.2.3)	X	X	X	X	X	X	X		
Body weight ^e	X			X		X (every 3 cycles)	X		
Hematology (see Table 4)	X	X ^f	X ^f	X ^f	X ^f	X ^f	X	X	
Clinical chemistry (see Table 4)	X	X ^f	X ^f	X ^f	X ^f	X ^f	X	X	
Urinalysis	X						X		
Prostate-specific antigen	X	X	X	X	X	X	X	X	
Testosterone level	X								
12-lead ECG ^g	X		X		X				
Circulating tumor cells ^h		X ^f	X ^f	X ^f	X ^f	X ^f	X		
cfDNA (blood) ⁱ	X		X ^f		X ^f		X		
Circulating soluble analytes/PK/ADA ^j	X	X ^f	X ^f	X ^f	X ^f		X		
Blood immune biomarkers ^j	X	X ^f	X ^f	X ^f	X ^f		X		
Archival tumor tissue	X								

Tests & Procedures	Screening/ Enrollment ^a	On-Treatment: Immunotherapy Combination Treatment					End of Treatment ^b	Follow up	
		Cycle 1	Cycle 2	Cycle 3	Cycle 4	Cycle 5 Onward			
Day		To be determined based on immunotherapy combination Refer to the cohort appendix for each respective combination for details on combination-specific timing						14 - 28 days after last dose	110 days after last dose
Window (days)	-28		± 3	± 3	± 3	± 3	± 7	± 10	± 14
Tumor biopsy ^k	X		X				X (at PD [optional]) ^k		
Stool collection ^l	X		X						
Concomitant medications	X	X	X	X	X	X	X	X	
Adverse events	All AEs/AESIs/SAEs will be collected for at least 100 days after the last dose of study intervention ^m								
Immunotherapy combination administration ⁿ		Refer to the cohort appendix for each respective combination for details on study intervention administration							

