Radiographic disease assessment	X	Per PCWG3 guidelines: Every 8 to 9 weeks (± 1 week) for first 24 weeks, and every 12 weeks (± 1 week) thereafter until radiographic PD or start of subsequent therapy. Refer to the cohort appendix for each respective combination for cohort-specific details							
Review of alternate anticancer therapy ^o								X	X
Follow-up for overall survival								X	X

ADA = anti-drug antibodies; AE(s) = adverse event(s); AESI(s) = adverse event(s) of special interest; cfDNA = cell-free deoxyribonucleic acid; ECG = electrocardiogram; ECOG = Eastern Cooperative Oncology Group; EOT = end of treatment; I/E = inclusion/exclusion; PCWG3 = Prostate Cancer Clinical Trials Working Group 3; PD = progressive disease; PD-1 = programmed cell death 1; PK = pharmacokinetics; Q3M = every 3 months; SAE(s) = serious adverse event(s)

^a Tests/procedures performed as standard of care prior to obtaining informed consent and within 28 days prior to the first day of study intervention administration do not have to be repeated at screening.

^b The End of Treatment Visit will be completed following the last dose of study intervention, either at completion of the on-treatment phase or at early discontinuation.

^c For up to 2.5 years from the initiation of study intervention, participants in the follow up phase will be contacted by the site to collect alternate anticancer therapy information and determine survival status.

^d Informed consent must be obtained prior to any study-specific procedures and may be obtained prior to the 28-day screening window.

^e Body weight may be required more frequently for study interventions using weight-based dosing. Combination-specific frequency will be provided in the cohort appendix for each respective combination.

^f Blood samples should be collected prior to administration of any study intervention.

^g 12-Lead ECG will be collected at screening, Cycle 2 and Cycle 4.

^h Circulating tumor cells will be collected at baseline (ie, Day 1 of Cycle 1 prior to study intervention administration), Day 1 of each cycle (prior to study intervention administration), and EOT.

ⁱ cfDNA (blood) will be collected at baseline (ie, screening visit prior to study intervention administration), Day 1 of Cycle 2 and Cycle 4, and EOT.

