5.4.2.1 Composite Response Rate

CRR is a composite endpoint where response is defined as a participant meeting at least one of the following:

- CTC response: Change from unfavorable (≥ 5 cells/7.5 mL of blood) to favorable (≤ 4 cells/7.5 mL of blood). Participants with a missing baseline CTC value or baseline CTC value < 5 cells/7.5 mL of blood will not be evaluated for this criterion. The baseline CTC value is defined as the last available value recorded prior to the first administration of study intervention.
- PSA response: Confirmed PSA response is defined as $\geq 50\%$ reduction in PSA from baseline, with a repeat assessment confirming the result at least 3 weeks later. Participants without a PSA value at baseline will not be evaluable for this criterion. The baseline PSA value is defined as the last available value recorded prior to the first administration of study intervention.
- Objective radiographic response (ORR): Best overall response of CR or PR by objective radiographic disease assessment of soft-tissue, non-bone lesions, as determined by PCWG3-modified RECIST version 1.1. Per RECIST, to be assigned a best overall response of CR or PR, changes in tumor measurements must be confirmed by a repeat radiographic assessment performed no less than 4 weeks after the criteria for initial radiographic response were first met. In addition, responders must not have bone lesions that have progressed, as determined by PCWG3 criteria. Participants with measurable disease at baseline who received at least 1 dose of any component of the combination study intervention but do not have evaluable RECIST assessments for any reason will be counted as not responding. Participants without measurable, soft-tissue disease at baseline will not be evaluable for this criterion.

Response rates will be estimated within each cohort and 95% CIs will be estimated using the Clopper-Pearson method. Response rates and 95% CIs will also be presented for each individual criterion of CRR (CTC response, PSA response, and ORR).

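### The 6-month analysis trigger falls before a week-24 radiographic response can be confirmed in the last-enrolled participants, and the SAP does not say how such pending responses are handled

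*SAP*

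**What the plan says.** **Trigger.** SAP 3.4 runs the primary analyses for each cohort after "all participants for a specific cohort have at least 6 months of follow-up from the date of first dose" or have left the study. The only later analysis it names is optional and limited to survival: "A survival analysis of long-term follow-up may be performed after the primary analysis has been completed".

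**Scans.** Protocol 1.3, Table 1 schedules radiographic assessment "Every 8 to 9 weeks (± 1 week) for first 24 weeks, and every 12 weeks (± 1 week) thereafter". Timing in a cohort appendix "will supersede the general overview provided here"; those appendices are not among the documents available.

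**Confirmation.** SAP 5.4.2.1 assigns CR or PR only if the change is "confirmed by a repeat radiographic assessment performed no less than 4 weeks after the criteria for initial radiographic response were first met". CRR is met by any one of CTC response, confirmed PSA response or confirmed radiographic response. Under SAP Table 3, the CRR denominator is everyone dosed.

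**Decision rule.** SAP 3.3 states: "If there are 6 or more responses in these 30 participants, then the immunotherapy combination will be considered worthy of further investigation". Neither SAP 3.3 nor SAP 5.7.1 gives a data cut for that count.

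**The concern.** The trigger, the scan schedule and the confirmation rule do not fit together for participants enrolled near the end of a cohort. Their week-24 scan falls just before the 6-month mark, and the scan that could confirm a response falls after it. Only confirmed responses count and the denominator keeps every dosed participant, so a response awaiting confirmation becomes a non-response by default. The SAP has no rule for this case.

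The study exists to estimate response rates for the design of later trials, so a downward bias in ORR and CRR touches its stated purpose. It could also change whether a cohort reaches 6 of 30. Because the study is open-label, a choice left unmade now would be made with the pending responses in view.

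**Working it through.** **1. The plan's own figures.** Inputs from SAP 3.3: continue if at least 2 of 15 respond, succeed if at least 6 of 30 respond, rates 10% and 25%.

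P(success) = sum over x = 2..15 of P(X1 = x) × P(X2 ≥ 6 − x), with X1 and X2 binomial, n = 15 each.

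- At 10%: 0.0684 (SAP: 0.07)
- At 25%: 0.7745 (SAP: 77%)
- Early termination at 10%: 1 − P(X1 ≥ 2) = 0.549 (SAP: 55%)

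All three reproduce.

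**2. Timing on the 8-week grid.** Six months = 365.25 / 2 / 7 = 26.1 weeks. Scheduled scans fall at weeks 8, 16, 24 and then 24 + 12 = 36.

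- First response at week 24, window 23-25.
- Earliest confirmation: 23 + 4 = 27 to 25 + 4 = 29 weeks, by an unscheduled scan.
- Scheduled confirmation: 36 ± 1 = 35-37 weeks.

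Both are later than 26.1 weeks.

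**3. Timing on the 9-week grid.** A response first seen at week 18 can be confirmed from week 22 if someone orders a repeat scan. If it waits for the next scheduled scan, that is week 27 (if the 9-week step continues) or week 30 (if the 12-week step starts). The window around week 27 is 26-28, so that scan may just precede 26.1 weeks. The response may be pending, but need not be.

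**4. Who is affected.** The trigger is a minimum set by the last participant, so those enrolled earlier have more follow-up. With uniform Stage 2 accrual over A weeks and a cut exactly at the trigger (rounded to 26 weeks), the share of Stage 2 participants short of week W is (W − 26) / A.

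- W = 36: 10/26 = 38%; 10/52 = 19%
- W = 28: 2/26 = 8%; 2/52 = 4%

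**5. Effect on the 6/30 rule.** The documents give neither an accrual rate nor the share f of composite responses that are radiographic-only and first seen at week 24. Assume A = 26-52 weeks and f = 10-30%, treat Stage 1 as complete, and suppose the 6/30 count is taken at this cut. The Stage 2 response probability becomes p × (1 − share × f).

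| Confirmation | A (weeks) | f | Stage 2 responses missed | Power | Type I error |
|---|---|---|---|---|---|
| None pending | – | – | 0 | 77.4% | 0.068 |
| Scheduled scan | 52 | 10% | 1.9% | 76.7% | 0.066 |
| Scheduled scan | 26 | 30% | 11.5% | 72.7% | 0.055 |
| 4-week repeat | 52 | 10% | 0.4% | 77.3% | 0.068 |
| 4-week repeat | 26 | 30% | 2.3% | 76.6% | 0.066 |

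The power loss is 0.7-4.8 points on scheduled scans and 0.1-0.9 points with 4-week repeats.

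**The case against.** The case against has several parts, and most of it limits the size of the problem.

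- **Only late enrolees are affected.** A reader might infer that every week-24 response in the cohort is lost. The trigger sets a minimum, not a cap, so Stage 1 and early Stage 2 participants can be confirmed. If all 30 were affected, power would be 41-73% for f = 5-30%, but the trigger does not produce that case.
- **A pending scan is not always a CRR failure.** CTC response needs no confirmation and CTC is drawn every cycle; PSA is also measured every cycle. Only a radiographic-only response is lost from CRR. ORR, reported separately with its own interval, has no such protection.
- **The 6/30 count is undated.** A reader might infer that the decision is fixed at the 6-month trigger. No section says so. CRR is among the analyses run then and no other date is given, but the link is an inference.
- **No later update is named, but none is forbidden.** The plan is silent on it, and the trigger also permits a later cut.
- **One-response margins.** Under a true rate of 25%, the chance of passing with exactly 6 responses is 13%. A reader might take that as the chance of a reversed decision. It is not, because one of the six must also be pending. The power loss above is the relevant measure.
- **The grid is a default.** Cohort appendices may change it.
- **Any finite cut leaves some responses unconfirmed, and the study is exploratory.** Both are true. Here, though, the cut falls just before confirmation of a response from a scheduled scan becomes possible, and the scan that would settle it is already scheduled.

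**Conclusion.** The point holds in a limited form. Under the default scan schedule, the earliest cut that SAP 3.4 permits comes before a week-24 CR or PR can be confirmed in the last-enrolled participants. Such a response is scored as a non-response in ORR, and in CRR when no other component qualifies, and no CRR or ORR update is specified.

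The bias is downward and small: 0.1-4.8 points of power across the assumed accrual and response patterns. Type I error falls slightly (0.068 to 0.055-0.068), so a combination is not made easier to pass. These figures depend on assumptions about accrual and f that the documents cannot check, on a cut taken exactly at the trigger, on the 6/30 count using that cut, and on the default grid applying. The timing mismatch and the missing rule do not depend on the assumptions about accrual and f.

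**What to change.** Choose one of two changes.

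1. **Fixed follow-up, in SAP 3.4.** Set the CRR and ORR cut at a minimum follow-up that includes the first scheduled scan after week 24: 36 + 1 = about 37 weeks from first dose, or the equivalent on the cohort appendix's grid, unless the participant has discontinued the study. State that the 6/30 count uses this cut.
2. **Keep the 6-month cut, with a rule in SAP 5.4.2.1.** Report responses awaiting confirmation separately at that cut. Pre-specify that CRR, ORR and the 6/30 count are finalised once the confirmatory assessments are in.

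Either is preferable to an analysis date that moves with the responses observed. Both use scans already scheduled and need only a sentence or two in the SAP. The cost is a delay of about 10-11 weeks in the final CRR and ORR (36 − 26 = 10; 37 − 26.1 = 10.9). Under the first option the delay applies to every cohort; under the second, only to a cohort with a response pending.
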